3. To measure the concentration of EPA and DHA in individual blood lipid classes (phospholipids, triacylglycerol (TAG), non-esterified fatty acids (NEFA) and cholesteryl esters (CE)) and blood cells (erythrocytes and peripheral blood mononuclear cells) in the blood of fasted healthy subjects following consumption of high omega 3 Camelina oil for 8 weeks compared with consuming an equivalent fish oil (similar EPA+DHA content) for the same time period. (Study B).
4. To measure in vitro immune responses (mononuclear cell mediator production, mononuclear cell and neutrophil phagocytosis and respiratory burst response, T cell signalling) by cells from the blood of fasted healthy subjects following consumption of high omega 3 Camelina oil for 8 weeks compared with consuming an equivalent fish oil (similar EPA+DHA content) for the same time period. (Study B).

9. The study

Subjects

For each study (A and B) we will recruit to enrol 10 healthy men and 10 healthy women each in two age ranges (18 to 30 years or 50 to 65 years). We estimate (based on past experience) that this will require screening of approximately 30 men and 30 women in each age group for each study⁵⁵.

For the purpose of this study healthy will be defined as having health screening results that are within normal ranges, a body mass index of 18.5-30.0 kg/m² and without diagnosis of chronic illness.

Inclusion criteria

1. Male or female
2. 18 to 30 years or 50 to 65 years
3. Body mass index 18.5-30.0 kg/m²
4. Health screening results that are within normal clinical ranges (systolic blood pressure ≤ 140 mm/Hg, diastolic blood pressure ≤ 90 mm/Hg, total cholesterol concentration < 7.5 mmol/L, random glucose concentration < 11 mmol/L)
5. Not consuming fish oil or other oil supplements
6. Not eating more than one oily fish meal per week
7. Willing to adhere to the study protocol
8. Being able to provide written informed consent

Exclusion criteria

1. Aged < 18 years; 31-49 years or > 65 years
2. Body mass index < 18.5 or > 30 kg/m²
3. Current smoker
4. Random sample blood cholesterol or glucose concentrations outside the normal concentration range
5. Diagnosed chronic illness (for example diagnosed cardiovascular disease, diabetes, cancer, rheumatoid arthritis)
6. Diagnosed food allergy.
7. Regular use of anti-inflammatory medication (e.g. aspirin, ibuprofen, diclofenac) or anti-coagulant therapy.

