The high omega 3 Camelina oil contains around 10% of fatty acids as EPA and 10% as DHA. It will be given incorporated into the high fat meal for study A and as dietary supplement oil for study B. Subjects will be randomised to allocate order of supplement. Subjects, researchers and clinical staff will be blinded to group allocation.

Subject participation schedule

Study A

Subjects who express an interest will be contacted by telephone or email. If they fit the inclusion and exclusion criteria they will be sent the information sheet. They will be contacted about 7 days later to confirm their interest or not. If they remain interested an appointment will be made for them to visit the NIHR Wellcome Trust Clinical Research Facility, Southampton General Hospital. At this first visit the study will be explained, any questions answered and written consent obtained; subjects will then have height, weight, and blood pressure measured and a screening blood sample collected (10 ml) to confirm that they meet the inclusion criteria. An appointment will be made for the subsequent clinic visit; one further clinic visit will be made (i.e. three clinic visits in total). Subjects will attend the 2 latter clinic visits in the fasted state (no food or drink except water after 8 pm the previous evening).

Subjects will visit the Wellcome Trust Clinical Research Facility, Southampton General Hospital on three occasions.

[figure not shown]
At the second and third visits the subjects will attend the clinic between 7 and 9 am and will have a cannula inserted into a forearm vein and a baseline blood sample (10 ml) collected. Subjects will then consume one of the test meals on each of two study visits in random order.

The composition of the test meals will be based upon typical UK nutrient intakes as we have used in previous post-prandial studies. The lipid component will be derived from a blend of fat sources (fish oil or high omega 3 Camelina oil, safflower oil, double cream, linseed oil and olive oil) to model the fatty acid profile of the UK diet. Approximately 450 mg EPA plus DHA will be provided by the oils (fish oil or high omega 3 Camelina oil) for the meal challenge (providing the recommended UK daily intake)¹⁷.

Blood samples (10 ml) will then be collected for 8 hours (at 30 minute intervals up to 3 hours and then hourly; total volume sampled 120 ml). A light meal (e.g. sandwiches) will be provided at the end of

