the visit. Subjects will then consume the other test meal at the next study visit which will be at least 14 days after the first. This will complete study A.

Study A

Study B

[figure not shown]
Subjects who express an interest will be contacted by telephone or email. If they fit the inclusion and exclusion criteria they will be sent the information sheet. They will be contacted about 7 days later to confirm their interest or not. If they remain interested an appointment will be made for them to visit the NIHR Wellcome Trust Clinical Research Facility, Southampton General Hospital. At this first visit the study will be explained, any questions answered and written consent obtained; subjects will then have height, weight, and blood pressure measured and a screening blood sample (10 ml) to confirm that they meet the inclusion criteria.

Subsequently four further clinic visits will be made. Subjects will attend each of these four clinic visits in the fasted state (no food or drink except water after 9 pm the previous evening).

Subjects will visit the NIHR Wellcome Trust Clinical Research Facility, Southampton General Hospital on five occasions the first to obtain consent and collect a screening blood sample, then to attend four study appointments, each between 8 and 11 am. On each occasion following the first visit they will be in the fasted state.

At the four subsequent study visits the subjects a blood sample (40 ml) will be collected. The first of these visits will be a baseline visit and the subject will receive either the fish oil or high omega 3 Camelina oil supplement (allocated by randomisation). The subject will return for the second study visit after consuming the supplement for 8 weeks. At study visit 2 a blood sample will be collected and the subject will commence the 6 week wash out period. After this period they will return for study visit 3 where a blood sample will be collected (as verification that the subject's blood fatty acid composition has returned to the values seen pre-supplementation) and the subject given the second supplement. The subject will consume this daily for 8 weeks and then return for study visit 4. This will complete study B.

Study B

Schedule of subject visits and activities performed at each visit

X indicates the activity will take place.

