Study B. Based upon our previous work¹⁸, ten subjects per group will provide 80% power for detecting a 40% increase in EPA or DHA in plasma phospholipids ($\alpha = 5\%$ and $\beta = 7.5\%$) in a two tailed test based upon after 30 days supplementation. Based upon our previous work¹⁹, ten subjects per group will provide 85% power for detecting a 10% increase in concanavalin A stimulated IL-4 and IL-2 secretion in vitro ($\alpha = 5\%$ and $\beta = 7.5\%$) in a two tailed test based upon after 30 days supplementation. In the first instance, data from the two phases of the cross over studies will be compared for time effects and if no significant time effects are detected, the data sets for each treatment will be combined¹⁸. Non-parametric data will be normalised by log transformation. The postprandial changes in plasma metabolites will be analysed by ANOVA with treatment, age and sex as fixed factors and time as a repeated measure. The effect of the different oils on plasma metabolites and immune function in the dietary supplementation study will be assessed by ANCOVA with baseline as a covariate.

13. Safety assessments

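### No blocking or stratification of oil order is stated and neither named model has a period term, so a missed period effect enters the oil estimate in proportion to the realised order imbalance

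*Combined protocol and SAP*

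**What the plan says.** Section 9, Subjects, fixes the composition of each study: "we will recruit to enrol 10 healthy men and 10 healthy women each in two age ranges". That makes four groups of ten, or 40 subjects per study.

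Section 9, Supplements, gives the allocation in one sentence: "Subjects will be randomised to allocate order of supplement". The Study A schedule adds that "Subjects will then consume one of the test meals on each of two study visits in random order". The Study B schedule says that the first oil is allocated by randomisation and that the other follows a 6-week wash-out. No ratio, blocking, stratification or method of producing the list is given.

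The analysis text is at the end of section 12. It starts with a preliminary check: "In the first instance, data from the two phases of the cross over studies will be compared for time effects". The rule that follows is that "if no significant time effects are detected, the data sets for each treatment will be combined". No significance level is given for this check, and no action is stated if it is significant. Study A's postprandial changes are to be "analysed by ANOVA with treatment, age and sex as fixed factors and time as a repeated measure". Study B's outcomes are to be "assessed by ANCOVA with baseline as a covariate". Neither model names period or sequence. In Study A, time as a repeated measure refers to the postprandial sampling times, not to the phase.

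**The concern.** Both studies are two-period crossovers. Without a period term, the mean within-subject oil difference is free of any phase-to-phase shift only if equal numbers take each oil first. Age and sex are used to set recruitment in both studies and as factors in the Study A model, but the documents do not say that they are used in allocation. A lopsided order, overall or within an age or sex group, would put part of any period shift into the oil comparison. The only safeguard in the text is the preliminary time test, which has little power in small groups.

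A period shift is most plausible in Study B, where the two phases start 14 weeks apart (8 weeks of supplement plus 6 weeks of wash-out). The aim is to judge whether the two oils are comparable, so a shift could either hide or mimic a difference.

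**Working it through.** **Plan's own figures.** The plan gives no figure for order balance or period effects. The power statements in section 12 give no standard deviation, so they cannot be reproduced; they are not needed here.

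**Inputs from the documents.** N = 40 per study, in four groups of 10 (so 20 per age group and 20 per sex); two periods; random order; no period term.

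**Assumptions.** Simple 1:1 randomisation; no carry-over; within-subject oil difference with residual SD 1; period effect of 0.25 or 0.5 of that SD; preliminary test at 5%.

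**Step 1: mechanism.** With n1 and n2 subjects in the two orders,

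mean within-subject oil difference = oil effect + period effect × (n1 − n2)/N.

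- 24:16 of 40: 8/40 = 20% of the period effect enters.
- 26:14 of 40: 12/40 = 30%.
- 14:6 of 20: 8/20 = 40%.

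**Step 2: chance of such splits (exact binomial, p = 0.5, both tails).**

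- N = 40: P(24:16 or worse) = 0.268; P(26:14 or worse) = 0.081. The mean of |n1 − n2|/N is 0.125.
- N = 20: P(14:6 or worse) = 2 × (1 + 20 + 190 + 1140 + 4845 + 15504 + 38760)/1048576 = 120920/1048576 = 0.115. For at least one of the two age groups: 1 − (1 − 0.115)² = 0.22.

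**Step 3: precision of the oil estimate at N = 40.** Over random splits without a period term, the variance is (1 + period effect²)/N. For a 0.5 SD period effect this is 1.25/40, a standard error of 0.177. With exact 1:1 balance it is 1/40, a standard error of 0.158. The ratio of variances is 1/1.25 = 0.80, so the loss equals dropping from 40 subjects to 32. Simulation (40,000 trials) gave the same 0.177 and 0.158, and 0.161 for simple randomisation with a period term.

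**Step 4: what the preliminary test misses (simulation).** At N = 40, a 0.25 SD period effect is missed in 66% of trials and a 0.5 SD effect in 13%. In a single group of 10, 0.5 SD is missed in 71%.

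**Step 5: type I error without a period term, N = 40 (simulation).**

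| Condition | 0.25 SD | 0.5 SD |
|---|---|---|
| Averaged over all splits | 0.050 | 0.051 |
| Split 26:14 or worse | 0.071 | 0.128 |
| Split 26:14 or worse, time test not significant | 0.055 | 0.063 |

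With a period term, the error in the 26:14-or-worse trials at 0.5 SD is 0.050.

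**Step 6: blocking without a period term.** The period effect cancels from the estimate but stays in the residual. At 0.5 SD the test becomes conservative (type I error 0.028). Power for a 0.5 SD oil effect is 0.81, against 0.87 when the term is added.

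**The case against.** The strongest reply has four parts.

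1. **Silence is not a statement.** A reader might infer that order is deliberately left unbalanced. The documents neither promise nor exclude blocking, so the probabilities above apply only if simple randomisation is used. This stands.

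2. **Pooling is conditional.** A reader might infer that any period effect contaminates the oil comparison, or that the trial's error rate is inflated. The text does not support that. The phases are tested first, random order keeps the estimate unbiased on average, and type I error averaged over splits is about 5%. Even with a 26:14 or worse split, error among trials passing the test is only 0.055 to 0.063. This also stands. Its limits are that the test is weak in small groups and that the plan does not say what follows a significant result.

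3. **Single-cell figures would mislead.** One can compute a 37% chance that at least one of the four cells splits 8:2 or worse, and an 81% chance for 7:3 or worse. The plan names no oil comparison within a single cell. For the two age groups of 20, the chances of the same shares (60% and 40%) in at least one group are 2% and 22%.

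4. **The period effect is unknown.** No size is documented. Study A's visits may be as little as 14 days apart, plasma and cells are frozen, which would permit batch assay, and season is a shared shift only if subjects start together. In Study B blood is drawn at the start of each phase, so a phase-specific baseline would absorb shifts already present then. The plan does not say which baseline is used. This limits the size of the concern but does not remove it, because whole-blood function tests may not be open to batching.

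**Conclusion.** The point holds in a limited form. The plan states no order balance within the strata it recruits, and it names two analyses without a period term, so balance matters for the result. Under simple randomisation the consequences are lost precision (standard error 0.177 instead of 0.158 for a 0.5 SD period effect at N = 40) and bias conditional on the realised split. For the 40-subject oil comparison the effect is modest. It matters more for results by age or sex, where a 14:6 split would carry 40% of a period effect that the preliminary test could easily miss. It is not a claim of bias on average or of overall type I error inflation. The sizes rest on simple randomisation, no carry-over, period effects of 0.25 to 0.5 SD of the within-subject difference, and a 5% preliminary test; the documents state none of these.

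**What to change.** State that order is randomised 1:1 in permuted blocks within each of the four age-by-sex groups, with separate lists for Study A and Study B. Use block lengths that add up to ten, so that a complete group splits 5:5.

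Include period as a term in both the Study A ANOVA and the Study B ANCOVA whatever the preliminary time test shows, and drop that test as a condition for pooling. Both parts are needed: blocking alone leaves period variance in the residual, and withdrawals, which section 13 provides for, can undo the balance. Say also which baseline the Study B ANCOVA uses.

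The cost is one degree of freedom and a stratified list prepared before enrolment. If there is no period effect, adding the term under simple randomisation raises the standard error at N = 40 only from 0.158 to 0.160; with balanced order it stays at 0.157 in the simulation.

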Visits 1 and 2 and 3 to 4 will be around 8 weeks apart and subjects will consume fish oil or high omega 3 Camelina oil daily during that period. Visits 2 to 3 will be a 6 week wash-out period.

Activity	Screening Visit	Study Visit 1	Study Visit 2	Study Visit 3	Study Visit 4
Subject fasted		X	X	X	X
Informed consent	X				
Height	X				
Weight	X	X	X	X	X
Blood for screening	X				
Blood for fatty acids, and in vitro immune and inflammatory responses		X	X	X	X

Sample analysis

Blood collected at study entry will be used for screening. This will be analysed by the University Hospital Southampton NHS Foundation Trust Chemical Pathology Laboratory for blood cholesterol and blood glucose.

Study A. At the 2 study visits blood will be used to prepare plasma, mononuclear cells and red cells. Plasma will be aliquoted and frozen at minus 80°C. Mononuclear cells and red cells will be frozen at minus 80°C. Lipid will be extracted from plasma and red cells using chloroform/methanol and fatty

acid composition determined using standard techniques. Size distribution and concentration of chylomicron, VLDL, LDL and HDL lipoprotein particles will be analysed by NMR in samples collected at baseline, 3 and 8 hours. Immune and inflammatory mediators will be measured in plasma using multiplex immunoassays.

Study B. At the 4 study visits blood will be used to prepare plasma, mononuclear cells and red cells. Plasma will be aliquoted and frozen at minus 80°C. Mononuclear cells and red cells will be frozen at minus 80°C. Lipid will be extracted from plasma and red cells using chloroform/methanol and fatty acid composition determined using standard techniques.

Plasma will be used to evaluate blood lipid concentration and particle sizes

Mononuclear cells will be cultured for 24-48 hours and immune mediators in response to stimulation measured in plasma will be measured using multiplex immunoassays and ELISA.

Whole blood will be used to investigate neutrophil phagocytosis and respiratory burst response to bacterial challenge. Whole blood will be used to measure mononuclear cell phagocytosis.

T cells from the mononuclear cells will be mitogen stimulated and the RNA harvested in prepared for microarray analysis of the T cell transcription.

Data will be compared across time and between groups by ANOVA with repeated measures.

10. Data handling and record keeping

- All data will be entered onto a spreadsheet (Microsoft Excel) by the researchers involved.

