- All data will be entered on a password-protected computer. This data will be accessed only by the PI and the researchers involved.
- All data will only be linked to study codes and thus not identifiable with the source volunteer. However, the caveat to this will be a data set recording the volunteer name and study code without any other volunteer details.
- All data recorded on paper will be kept in a locked filing cabinet in the researchers' office and/or in a dedicated, restricted access, clinical data storage area on Level D of the IDS Building, University of Southampton.
- Data of an identifiable nature (i.e. volunteer names, contact details, addresses) will be destroyed 12 months after the end of the study. All other data will be kept securely for 15 years and then destroyed.
- Data will be obtained, handled and stored in adherence to the principle set out in the Data Protection Act 1998.
- The investigators will permit monitoring, audits, REC and MHRA review (as applicable) and provide direct access to source data and documents.

11. Statistical Analysis

The statistical analysis will involve the comparison of inflammatory markers (proteins, lipids etc) and of fatty acids between fish oil and High omega 3 Camelina oil supplements. All statistical comparisons will be performed at the end of the study using SPSS version 21 (or later).

12. Sample size calculation

Study A. Based on our published findings¹⁶, ten subjects per group will provide 85% power for detecting a 10% difference in peak postprandial concentrations of EPA or DHA in plasma TAG at $\alpha = 5\%$ and $\beta = 7.5\%$ in a two tailed analysis. Based on our previous findings of the effect of consuming a FO-enriched meal on lipoprotein size and concentration¹⁷, Ten subjects per group will provide 85% power for detecting 13 nmol/l difference in peak postprandial VLDL concentration and 11 nm difference in VLDL particle size ($\alpha = 5\%$ and $\beta = 7.5\%$) in a two tailed analysis. Based on our preliminary data, ten subjects per group will provide 80% power for detecting a maximum change of 0.8pg/ml IL-6 (30% difference) in a two-tailed test ($\alpha = 5\%$ and $\beta = 20\%$).

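### Study B samples blood at Visit 3 to verify wash-out, but the plan sets no Visit 3 versus Visit 1 comparison, leaves the period-2 baseline undefined, and pools the phases on a non-significant time-effects test

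*Combined protocol and SAP*

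**What the plan says.** Study B is a two-period crossover (Section 9, Supplements: "Subjects will be randomised to allocate order of supplement"). Section 9, Study B and its visit schedule, sets the timing: "Visits 1 and 2 and 3 to 4 will be around 8 weeks apart", and "Visits 2 to 3 will be a 6 week wash-out period". Fasting blood for fatty acids and immune measures is scheduled at all four study visits. The Visit 3 sample has a declared purpose, to verify that the subject's "blood fatty acid composition has returned to the values seen pre-supplementation) and the subject given the second supplement".

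On when results exist, Section 9 (Sample analysis) says "Plasma will be aliquoted and frozen at minus 80°C", with cells also frozen, and Section 11 says "All statistical comparisons will be performed at the end of the study using SPSS version 21 (or later").

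The analysis text is at the end of Section 12. The two phases are first compared for time effects, and "if no significant time effects are detected, the data sets for each treatment will be combined". Study B is then analysed by covariance analysis adjusting for baseline. Section 9 (Sample analysis) separately mentions a repeated-measures ANOVA over time and between groups.

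On what baseline means, Section 9 says of the four study visits that "The first of these visits will be a baseline visit". It does not use that word for Visit 3.

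**The concern.** The protocol collects a sample specifically to show that wash-out is complete, then gives no rule for using it. There is no definition of having returned, no tolerance, no comparison of Visit 3 with Visit 1, and no consequence if values are still raised. What stands before pooling is a test of whether the phases differ, which addresses a different question.

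This matters because the residue need not be the same in both orders. If what remains is proportional to the first-period rise, it is unequal whenever the two oils raise EPA and DHA by different amounts, and that is what Study B is meant to find out. The background text before Section 8 itself suggests that the Camelina fatty acids may be released more readily. Shrinkage of the oil difference would favour a finding that the oils are comparable, which is the stated aim. Objective 3 in Section 8 covers erythrocytes and mononuclear cells as well as plasma lipid classes, so adequate wash-out in one pool cannot be presumed for all.

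**Working it through.** **Inputs from the documents.** Periods of 8 weeks and a wash-out of 6 weeks (Section 9). Forty subjects per study: 10 men and 10 women in each of two age ranges (Section 9, Subjects). Ten per group, 80% power and a 40% increase in plasma phospholipid EPA or DHA (Section 12). **Assumed, because not given:** half-life, SD, within-subject correlation, and 20 subjects per order.

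**Step 1. Effect of residue on the oil difference.** Let A and B be the true 8-week rises on the two oils. Let the first rise decay exponentially, so that a fraction r(t) = 2^(−t/h) remains t weeks after Visit 2. Then r6 remains at Visit 3 and r14 (6 + 8 weeks) at Visit 4.

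- Order A then B: Visit 3 = A·r6, Visit 4 = B + A·r14.
- Order B then A: Visit 3 = B·r6, Visit 4 = A + B·r14.

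Averaging each oil over the two orders and subtracting gives:

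- End-of-period values, or Visit 1 as the only baseline: (A − B)(1 − r14/2).
- Change from Visit 3: (A − B)(1 + (r6 − r14)/2).
- Covariance adjustment for Visit 3 with slope b: (A − B)(1 − (r14 − b·r6)/2).

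| Half-life (weeks) | r6 | r14 | End-of-period | Change from Visit 3 | Adjusted, b = 0.5 |
|---|---|---|---|---|---|
| 2 | 0.125 | 0.008 | −0.4% | +6% | +3% |
| 4 | 0.354 | 0.088 | −4% | +13% | +4% |
| 6 | 0.500 | 0.198 | −10% | +15% | +3% |
| 8 | 0.595 | 0.297 | −15% | +15% | 0% |

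Example at 4 weeks: 1 − 0.088/2 = 0.956; 1 + (0.354 − 0.088)/2 = 1.133; 1 − (0.088 − 0.177)/2 = 1.044. For b from 0.3 to 0.7 the adjusted estimate stays within about −6% to +8%. With a 1-week half-life, r6 is 1.6% and every bias is under 1%.

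**Step 2. What the time-effects test sees.** With equal orders and end-of-period values, residue makes the mean phase difference r14(A + B)/2, while the bias in the oil comparison is −r14(A − B)/2. The test therefore responds to average residue, not to the difference between oils. It also cannot separate residue from a genuine period effect.

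**Step 3. Its power.** No SD is given, so the stated 80% cannot be reproduced independently. Solving for the SD gives 40/((1.960 + 0.842)·√(2/10)) = 31.9 percentage points. With correlation ρ, the SD of a paired difference is 31.9·√(2(1 − ρ)), which is 31.9 at ρ = 0.5. A Visit 4 residue of 20% or 30% of a 40-point rise is 8 or 12 points, close to the r14 values for 6 and 8 weeks. By paired t-test, two-sided 5%:

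- n = 40, ρ = 0.5: power 34% and 64%.
- n = 40, ρ from 0.3 to 0.7: 26–51% and 50–85%.
- n = 10, ρ = 0.5: 11% and 19%.

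The same Section 12 sentence also gives β as 7.5%, which conflicts with 80% power. Taken as 92.5% power, it implies an SD of 40/((1.960 + 1.440)·√(2/10)) = 26.3, and the n = 40, ρ = 0.5 powers become 47% and 80%.

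**Step 4. Precision of period 1 alone.** With 20 per order and outcome variance σ², the variance is 2σ²/20 = σ²/10. The crossover with 40 subjects has 2σ²(1 − ρ)/40 = σ²(1 − ρ)/20. The ratio is 2/(1 − ρ), which is 4 at ρ = 0.5, so the standard error doubles. This is before any baseline adjustment.

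**The case against.** A reader might infer three stronger things, and the documents support none of them.

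- *That Section 12 never uses the Visit 3 value.* The baseline in the covariance analysis may well be Visit 3 for period 2. Study A takes a baseline sample at each of its two test visits, and the repeated-measures ANOVA could also include Visit 3. The text is ambiguous, not silent.
- *That the verification cannot act because the second oil is handed over at the same visit.* The protocol never says the result was to decide whether dosing proceeds. A retrospective check fits frozen samples and end-of-study comparisons. What is missing is the content of that check.
- *That carry-over goes wholly unchecked.* Residue common to both oils would appear as a phase difference, so the time-effects test is a real safeguard, though a weak and non-specific one.

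Two limits on the size also stand. With equal numbers per order, equal residue cancels, so the bias is proportional to A − B and vanishes if the oils are equal. And the 10–15% figures are extremes; the analysis most naturally read from Section 12, if its baseline is Visit 3, gives much smaller bias at moderate slopes. The pooling rule also cites a reference that may justify it and cannot be seen here; reference number 18 appears twice in the list.

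These points narrow the concern without closing it. Both the direction and the size of the bias depend on a baseline definition that the plan omits.

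**Conclusion.** The concern holds in this form: the wash-out sample has no planned comparison, the period-2 baseline is undefined, and pooling rests on a non-significance test that can miss moderate residue, does not address carry-over differing between oils, and has no rule for a significant result.

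The possible distortion of the oil difference runs from negligible at half-lives of 1 to 2 weeks with end-of-period values to about 15% in either direction at 8 weeks, depending on the baseline used. It rests on exponential loss, residue proportional to the first rise, equal orders, and half-lives that are assumptions throughout. The documents do not show that wash-out is incomplete. They show that the plan would not reveal it clearly if it were. This should be corrected, but it does not undermine the design.

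**What to change.** Leave the visit schedule as it is and change the Section 12 analysis text:

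1. Replace the significance-gated pooling with a crossover model that always contains oil and period, with subject as the blocking factor.
2. State which visit is the baseline for period 2, and reconcile this with the Section 9 wording and with the repeated-measures ANOVA given there.
3. For each fatty-acid pool, report Visit 3 minus Visit 1 by order of oils, with a 95% confidence interval.
4. Report a period-1-only comparison (Visit 2 adjusted for Visit 1) as a pre-planned sensitivity analysis, always shown beside the crossover estimate and never selected by a preliminary test.

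A period term does not itself remove unequal carry-over; items 3 and 4 show whether it matters. The cost is plan wording and a few extra analyses of data already being collected. The period-1 estimate is free of carry-over but clearly less precise, with about double the standard error under the assumptions in the working, so it should be read as a check on the crossover result and not as its replacement.

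### Study A's 85% power is stated for a peak EPA or DHA value, but no test or definition of that peak is specified; the stated repeated-measures ANOVA tests something else

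*Combined protocol and SAP*

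**What the plan says.** All references are to the combined protocol and SAP.

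- **Section 12, Study A:** ten subjects per group are said to give 85% power for a 10% difference in "peak postprandial concentrations of EPA or DHA in plasma TAG", "in a two tailed analysis" at a 5% level. The basis is given only as "Based on our published findings". The same paragraph powers peak VLDL concentration and VLDL particle size (85%) and a maximum change in IL-6 (80%).
- **Section 12, closing sentences:** postprandial changes in plasma metabolites will be "analysed by ANOVA with treatment, age and sex as fixed factors and time as a repeated measure".
- **Section 9, Sample analysis:** a general sentence also names repeated-measures ANOVA. Lipoprotein particles are measured by NMR at 0, 3 and 8 h only.
- **Section 9, Study A schedule:** after a baseline sample, blood is taken over 8 h "at 30 minute intervals up to 3 hours and then hourly", 120 ml in total. Each subject eats both meals, in random order, at least 14 days apart.
- **Section 11:** fatty acids and inflammatory markers will be compared between oils. No summary measure is named.
- **Section 8:** the postprandial aim covers the size of the EPA+DHA increase in plasma lipids and its turnover.

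**The concern.** The power statement is about one number per subject per meal. The planned model uses the whole curve and tests different quantities. A power figure holds only for the test and endpoint it was worked out for, so the reader cannot tell what the 85% applies to.

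Two things are at stake. First, the quantity that justified the sample size has no pre-specified estimate or confidence interval. Second, with two fatty acids, several lipid classes and 12 time points, an undefined peak leaves its definition (each subject's own maximum, or the value at a fixed time) and the choice of comparison open until after the data are seen.

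**Working it through.** **1. The plan's own figure.** Inputs from section 12: n = 10 per group, difference 10%, two-sided alpha 5%, power 85%. No SD is given, so the 85% cannot be reproduced; only the SD that would produce it can be found.

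- Two-sample, normal: SD = 10 / [(1.960 + 1.036) × √(2/10)] = 7.5%. With the t distribution, 7.1%.
- Paired, normal: SD of differences = 10 × √10 / (1.960 + 1.036) = 10.5%. With the t distribution, 9.4%.
- The same sentence gives beta as 7.5%, which means 92.5% power, not 85%. At 92.5% the four SDs become 6.6%, 6.2%, 9.3% and 8.2%.
- Two-sample normal power at n = 10 by assumed SD: 5% gives 99%, 7.5% gives 85%, 10% gives 61%, 20% gives 20%.

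**2. What the ANOVA's main effect averages.** Times from section 9: 0; 0.5 to 3 h in half-hours (6); 4 to 8 h hourly (5). Total 1 + 6 + 5 = 12, and 12 × 10 ml = 120 ml, as stated. Seven samples lie at or before 3 h.

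- Share of an unweighted mean carried by those seven: 7/12 = 58%.
- Trapezoidal weights in hours: 0.25 at 0 h; 0.5 at each of 0.5 to 2.5 h; 0.75 at 3 h; 1 at each of 4 to 7 h; 0.5 at 8 h; sum 8.
- Share of the AUC carried by the same seven: (0.25 + 5 × 0.5 + 0.75)/8 = 3.5/8 = 44%.

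The main effect is therefore neither a peak nor a total appearance over 8 h. If changes are taken from baseline, 11 times remain and the point is the same.

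**3. Does 85% carry over? An illustration only.** Everything in this step is assumed: ten subjects taking both meals; an excursion proportional to (t/4)·exp(1 − t/4), peaking at 4 h; SD of differences 9.4% of peak at every time, chosen so that a paired test at 4 h has 85% power; noise correlation 0.5, 0.8 or 0.95 per hour. Treatment-by-time uses the Greenhouse-Geisser correction, with 3,000 simulated trials per case.

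| Where the oils differ | Main effect | Treatment by time |
|---|---|---|
| In proportion along the curve, 10% | 66% to 97% | 35% to 95% |
| Only at 4 to 5 h, by 10% of peak | 9% to 15% | 60% to 100% |
| From 3 h on, by 10% of peak | 37% to 79% | 87% to 100% |

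With the peak-time test fixed at 85%, the ANOVA's tests fall on either side of it, depending on inputs the documents do not give.

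**The case against.** The strongest defence is that the time course is itself an objective. Section 8 asks for increase and turnover over 8 h, repeated-measures ANOVA suits that, and a single peak says nothing about turnover. Unequal spacing is no fault when time is a categorical factor. Section 11 does not rule out a peak comparison, and a per-time contrast from the model could include the time of the peak. All of this stands. It is a reason to keep the ANOVA, but it does not supply a definition or test for the quantity that was powered.

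Three stronger readings are tempting, and the documents do not support them.

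- **That the peak will never be tested.** The text supports only that no test of it is specified.
- **That averaging over time shrinks the 10% difference.** If the oils differ in proportion to the excursion, the mean excursion also differs by 10%. The absolute difference is smaller, but that is true of any time average. For assumed curves [(t/p)·exp(1 − t/p)]^k with peak p from 3 to 6 h and k = 2 or 3, the 12-point mean is 0.49 to 0.61 of the peak, and the trapezoidal mean is itself only 0.53 to 0.71.
- **That spreading the signal over 11 degrees of freedom leaves the ANOVA underpowered.** That holds only if the other times add no information, which step 3 shows need not be so. It also ignores enrolment. Section 9 plans 10 men and 10 women in each of two age ranges, 40 in all, each taking both meals, and section 12 does not say what a group is. If ten pairs give 85% on one degree of freedom (noncentrality 8.98), the same effect in 40 has 4 × 8.98 = 35.9, or about 99% power even on 11 (large-sample approximation).

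**Conclusion.** The mismatch holds. Section 12 powers a peak, and the plan states a repeated-measures ANOVA and specifies neither a definition nor a test of the peak. The 85% does not belong to the planned test. This conclusion rests on the text and the sampling schedule alone, not on an assumed curve.

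No size or direction can be put on the effect on power. That would need the SD, the within-subject correlation over time, the shape of the difference and the meaning of a group, none of which the documents give. The simulated ranges show only that the figure does not transfer.

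The gap is not confined to plasma TAG: no test is specified for peak VLDL concentration or the maximum IL-6 change either. For VLDL the 12 times do not apply, since NMR is done at three. The point should be settled before analysis, but it does not threaten the data, because the samples needed are already scheduled.

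**What to change.** 1. Define the peak in plasma TAG for each subject and visit, for EPA and for DHA separately, as powered. Say whether it is the subject's own maximum or the value at a fixed time.
2. Pre-specify a within-subject comparison of that peak between oils: treatment, period, sequence, age group and sex as fixed effects, subject as random, reported with a confidence interval.
3. Add incremental AUC over 0 to 8 h (trapezoidal) as the measure of total appearance.
4. Keep the repeated-measures ANOVA for the time course and the turnover aim.
5. Do the same for the maximum IL-6 change. For VLDL, define the peak from the 0, 3 and 8 h samples that are actually measured.
6. If the ANOVA is to stay the main test, restate the power for the effect it tests. On either route, give the SD, say what a group is, and reconcile 85% power with a beta of 7.5%.

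Cost: SAP wording, a little more analysis, and one more pre-specified comparison to report. No extra visits, samples or subjects are needed.
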